Document Date: April 7, 2020

EFFECT OF EXPIRATORY MUSCLE TRAINING ON STOMATOGNATHIC SYSTEM IN PATIENTS WITH STROKE

[name] PT, PhD¹. [name], PT, Assoc. [name]. [name],
Assoc. [name].

STUDY PROTOCOL

The aim of this study was to analyze and assess the effect of expiratory muscle training on the stomatognathic system in patients with stroke. Total of 31 individual included as 16 control and 15 study group to the study. Temporomandibular joint range of motion, masticatory muscle pressure pain threshold, facial asymmetry existence, head posture, oral hygiene health and habit, masticatory performance, intraoral pH, deglutition function and deep neck flexor muscle endurance of the individuals was assessed in order by; digital caliper, algometry, labial commissure and craniocervical angle measurement, general oral health assessment index and questionnaire, sieve test, digital pH gauge, repetitive saliva swallow test and, eating assessment tool and deep neck flexor endurance test. While study group was enrolled to 3-week respiratory muscle training in addition to conventional physiotherapy, control group enrolled to the conventional physiotherapy programme.

NCT NUMBER: NCT04569968

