Document Date: April 7, 2020

EFFECT OF EXPIRATORY MUSCLE TRAINING ON STOMATOGNATHIC SYSTEM IN PATIENTS WITH STROKE

[name] PT, PhD¹. [name], PT, Assoc. [name]. [name],
Assoc. [name].

Statistical Analysis

SPSS 22.0 was used for the data analysis. While constant variables were given as mean \pm standard deviation, categoric variables were given as number and percentage. If the parametric test conjectures were ensured, materiality test between two means was used for independent group variable comparison. If the parametric test conjectures were not ensured Mann-Whitney U test was used for independent group variable comparison. In dependent group analyses, materiality test was used between two couples in case parametric test conjectures were ensured, if the parametric test conjectures were not ensured Wilcoxon test was used.

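### Does the present/absent label on facial asymmetry leave that outcome without a usable analysis?

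*Protocol*

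**What the plan says.** The Study Protocol gives a list of nine outcomes and then a list of instruments, linked by the phrase "was assessed in order by". The third outcome is "facial asymmetry existence". Reading the two lists in parallel, it is matched to the first part of "labial commissure and craniocervical angle measurement"; the second part belongs to head posture. The group sizes are given as "Total of 31 individual included as 16 control and 15 study group".

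The Statistical Analysis section of the SAP says that "categoric variables were given as number and percentage". Between groups it offers two tests. Where parametric assumptions hold, "materiality test between two means was used for independent group variable comparison"; where they fail, "Mann-Whitney U test was used for independent group variable comparison". Within groups it offers a paired test of means or the Wilcoxon test on the same rule. It mentions no chi-square, Fisher or McNemar test, and neither document gives a threshold at which a face counts as asymmetric.

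**The concern.** The name of the outcome and its instrument point in different directions. The name suggests present or absent; the instrument yields a number. The other eight outcomes are not named in this way.

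If the analyst took the name literally, three things would be missing: the cut-off, a between-group test meant for categorical data, and much of the power that the measured value has in 31 patients. If the choice between the two scales were left until the data had been seen, the better-looking result could be reported, and the false-positive rate for this outcome would exceed its nominal level.

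**Working it through.** **Plan's own figure.** 16 + 15 = 31, as stated. The documents give no alpha, SD, effect size, power or sample-size calculation, so nothing else can be reproduced.

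**Reading the lists side by side.**

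| Order | Outcome | Instrument |
|---|---|---|
| 1 | Jaw joint range of motion | Digital caliper |
| 2 | Masticatory pressure pain threshold | Algometry |
| 3 | Facial asymmetry | Labial commissure measurement |
| 4 | Head posture | Craniocervical angle |
| 5 | Oral hygiene | Oral health index and questionnaire |
| 6 | Masticatory performance | Sieve test |
| 7 | Intraoral pH | pH gauge |
| 8 | Deglutition | Saliva swallow test and eating assessment tool |
| 9 | Deep neck flexor endurance | Endurance test |

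The pairing runs cleanly from first to last, so facial asymmetry is recorded as a measurement. The absence of a cut-off fits that reading: a measured outcome needs none, whereas a dichotomised one cannot be produced without one.

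**What a present/absent analysis would cost.** Assumptions not in the documents: normal measurement, equal SDs, two-sided 5%, higher mean in the group of 16. Let d be the true difference in SD units.

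The t-test has 29 degrees of freedom and critical value 2.045. Its noncentrality is d × √(16 × 15 / 31). At d = 1.04 this is 1.04 × 2.782 = 2.894, and power is 0.799. At d = 0.8 power is 0.576; at d = 1.2 it is 0.897.

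For a cut at c, measured in SDs from the midpoint of the two means, the proportions above it are 1 − Φ(c − d/2) and 1 − Φ(c + d/2). Power is the sum of the binomial probabilities of all 17 × 16 tables with p ≤ 0.05. At d = 1.04:

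| Cut | Proportions above | Fisher | Mann-Whitney on 0/1 data |
|---|---|---|---|
| Median of higher-mean group (c = 0.52) | 0.500 vs 0.149 | 0.444 | 0.57 |
| Midpoint (c = 0) | 0.698 vs 0.302 | 0.535 | 0.56 |
| Midpoint + 1 SD (c = 1) | 0.316 vs 0.064 | 0.311 | 0.46 |

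The Mann-Whitney column uses the tie-corrected, continuity-corrected normal approximation. Fisher's test is conservative at these sizes: its actual error rate is about 2.7-3.0% when both groups share a proportion between 0.2 and 0.5. So the Fisher column mixes the cost of dichotomising with the cost of that test, which the SAP does not name.

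**What choosing the scale after the fact would cost.** Simulating under no difference (300,000 trials of 16 versus 15), I counted how often the t-test or Fisher's test reached p ≤ 0.05. The t-test alone gave 5.0%; adding one fixed cut at the mean gave 6.3%; adding cuts at 0, 0.5 and 1 SD gave 9.0%.

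**The case for a change.** The best case for acting is that the text really is open. The name points to a yes/no variable, no sentence says the measurement is what gets analysed, and the SAP treats categorical variables separately and only as counts and percentages. Mann-Whitney can be run on 0/1 data, but the SAP ties it to failed parametric assumptions and not to categorical outcomes. Closing the gap would take one sentence in each document and no new data.

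All of that stands as a description of the text, and the power loss from dichotomising is real: even the kinder Mann-Whitney figures are well below 80%. What does not stand is the step from an open phrase to a defect in the analysis. The argument rests on one word in a translation that elsewhere writes constant for continuous, materiality for significance and conjectures for assumptions. The remedy would only restate what the listed instrument and listed tests already imply. The inflation argument needs someone to switch scales after seeing the data, which neither document suggests. With a single cut it adds little more than one percentage point to one of nine outcomes, none of them marked as primary.

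**Conclusion.** No change is called for. The ambiguity is genuine but is one of wording. On the natural reading, the labial commissure measurement is compared between groups by the SAP's test of two means or by Mann-Whitney, and nothing is lost. If counts of patients with asymmetry are also shown, the SAP's number-and-percentage rule covers them as description.

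The loss would arise only on the less likely reading. At 1.04 SD, power would go from 80% to 31-54% with Fisher or 46-57% with Mann-Whitney over the three cuts shown. These figures rest on assumed normality, equal SDs, a 5% level and an assumed effect; only the group sizes come from the documents. They show why the measured value is the better choice, and the plan as most simply read already uses it.

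### Does calling the study-arm programme respiratory rather than expiratory muscle training leave the tested intervention in doubt?

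*Protocol*

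**What the plan says.** The Protocol is a single paragraph under the heading Study Protocol. It opens with the aim, to "analyze and assess the effect of expiratory muscle training on the stomatognathic system in patients with stroke". The title, repeated at the head of the SAP, is "EFFECT OF EXPIRATORY MUSCLE TRAINING ON STOMATOGNATHIC SYSTEM IN PATIENTS WITH STROKE".

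The last sentence of the Protocol paragraph sets out the two arms. The "study group was enrolled to 3-week respiratory muscle training in addition to conventional physiotherapy", while the "control group enrolled to the conventional physiotherapy programme". Three weeks is the only detail given of the added programme.

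The Statistical Analysis section of the SAP does not mention the intervention. It gives the tests between groups and within groups, and nothing in it depends on what the programme is called.

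**The concern.** The arm sentence is where a reader looks to learn what was tested, and its term differs from that of the title and aim. Respiratory muscles include the inspiratory ones, so a programme under that label could train inspiration, expiration or both. Since no training content is described, the reader has only the label to go on.

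What would be at stake is attribution. The design compares physiotherapy plus an added programme with physiotherapy alone, so it estimates the effect of the whole addition. If the addition contained more than expiratory training, a difference between arms on any outcome could not be credited to expiratory training. The aim as worded would then go unanswered, and no test in the SAP could repair that.

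**Working it through.** The documents give no figure on this point, so the check is a comparison of wording followed by a look at what the contrast estimates.

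**Every mention of the intervention**

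| Place | Term |
|---|---|
| Protocol, title | expiratory muscle training |
| SAP, title | expiratory muscle training |
| Protocol, aim | expiratory muscle training |
| Protocol, study-arm sentence | respiratory muscle training |

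That is three mentions of the narrower term and one of the wider. The SAP title matches the Protocol title, so the Protocol and the SAP do not conflict. The variation lies inside the Protocol.

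**Are the terms incompatible?** No. Expiratory training is one kind of respiratory training, so all four mentions can be true of one programme. A contradiction would need a term that excludes expiratory training, or a passage naming a further component. Neither document has one: there is no mention of inspiratory training, of a second exercise or of a combined programme.

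**What the contrast estimates.** Let P be the effect of conventional physiotherapy, taken as the same in both arms, E the effect of expiratory training added to it, and X the effect of anything else in the added programme, including any interaction.

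- Study arm: P + E + X
- Control arm: P
- Difference: (P + E + X) − P = E + X

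If the programme is expiratory training only, X = 0 and the difference is E, which is what the aim asks for. If it has another component, the difference is E + X and two arms cannot split it. The comparisons within groups do not help, because the change within the study arm also carries X. The loss of attribution therefore depends wholly on X being present, and the documents give no sign of it.

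**What the word can alter.** The Protocol reports the groups thus: "Total of 31 individual included as 16 control and 15 study group to the study". The sum is right (16 + 15 = 31) and does not depend on the label. The same holds for the choice between the parametric test and its rank-based alternative. The documents state no power, significance level or target difference that the label could affect.

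**The case for a change.** The best case for acting is that the arm sentence is the operational one, and it uses the less specific term. An intervention should be identifiable from its protocol. Here there is no description of training content to fall back on, so even a reader who accepts the harmless explanation cannot confirm it. The remedy would also be cheap: one term throughout, checked against what was delivered, with no new data or analysis.

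Part of this stands. The wording is inconsistent, the quoted text is current, and neither document links the two terms. The programme is also thinly described. But replacing one word would not cure that, since the content would remain unstated whichever term was used.

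The step from inconsistent wording to a doubtful conclusion does not stand. It needs a component that no passage mentions. Loose language is the likelier explanation, because the English is imprecise elsewhere. The SAP calls what are evidently continuous variables constant, speaks of conjectures where assumptions are meant, and describes its parametric comparisons as materiality tests. In such a text, one general word in place of a specific one is weak evidence that the treatment differed. It is also too strong to say, without that condition, that attribution is affected for every outcome. That would be so only if X were present.

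**Conclusion.** No change to the plan follows. The mismatch is real but clerical: one mention in four uses a wider term that includes the narrower one. On the natural reading, its effect on sample size, tests, estimates and conclusion is nil.

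This rests on one assumption, that the arm sentence and the aim describe the same programme. The documents support it by context but do not prove it, and I take no position on which term is right. The authors know what was delivered, and a competent report would use one term to match it and word the conclusion for that programme added to conventional physiotherapy. Had either document mentioned a further training component, the judgement would be different, because the contrast would then be E + X and the aim would claim more than the design can show.

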Document Date: April 7, 2020

EFFECT OF EXPIRATORY MUSCLE TRAINING ON STOMATOGNATHIC SYSTEM IN PATIENTS WITH STROKE

[name] PT, PhD¹. [name], PT, Assoc. [name]. [name],
Assoc. [name].

Statistical Analysis

SPSS 22.0 was used for the data analysis. While constant variables were given as mean \pm standard deviation, categoric variables were given as number and percentage. If the parametric test conjectures were ensured, materiality test between two means was used for independent group variable comparison. If the parametric test conjectures were not ensured Mann-Whitney U test was used for independent group variable comparison. In dependent group analyses, materiality test was used between two couples in case parametric test conjectures were ensured, if the parametric test conjectures were not ensured Wilcoxon test was used.

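### The only between-arm test named is unadjusted and its variable is not named; if patients were randomised, ANCOVA on baseline would generally be more precise

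*SAP*

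**What the plan says.** The Statistical Analysis section of the SAP gives one between-arm comparison with two routes. Where parametric assumptions hold, a "materiality test between two means was used for independent group variable comparison"; I read this as the independent-samples t test. Otherwise: "If the parametric test conjectures were not ensured Mann-Whitney U test was used for independent group variable comparison".

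The other tests are within-arm: "In dependent group analyses, materiality test was used between two couples in case parametric test conjectures were ensured", and "if the parametric test conjectures were not ensured Wilcoxon test was used". No covariate, regression or baseline adjustment appears anywhere.

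The protocol gives the group sizes ("Total of 31 individual included as 16 control and 15 study group to the study") and lists the assessments (for example "deglutition function and deep neck flexor muscle endurance of the individuals was assessed in order by", followed by the instruments), but no assessment times. It describes the arms ("While study group was enrolled to 3-week respiratory muscle training in addition to conventional physiotherapy", while "control group enrolled to the conventional physiotherapy programme") without saying how patients were allocated. That each patient has a baseline and a post-training value is an inference from the paired and Wilcoxon tests.

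**The concern.** The aim is the effect of expiratory muscle training. Both arms receive conventional physiotherapy, so a within-arm test cannot separate training from physiotherapy or natural recovery. Only the comparison of 16 with 15 patients can, and the SAP leaves two things open there.

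First, the compared variable could be the baseline value, the post-training value or the change. The last two are both readings of the effect test, and their precision can differ widely, so a reader cannot tell which difference is reported.

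Second, whichever is meant, baseline is not used as a covariate. With 31 patients precision is scarce, and the analyst does not know beforehand which unadjusted choice will be the better one. ANCOVA largely removes that gamble. What is at stake is lost precision and an undefined estimate, not an invalid test.

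**Working it through.** **Inputs from the documents.** 16 control and 15 study patients; 16 + 15 = 31, which agrees with the stated total. There is no sample-size calculation, so no design figure to reproduce.

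**Assumptions, since the documents give no figures.** Random allocation, two-sided 5%, normal data, equal SDs at both times and in both arms, no dropout, true effect 0.8 SD. The baseline to post-training correlation r is varied.

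**Formulas.** The standard error for post-training values is sqrt(1/16 + 1/15) = 0.359 SD. Variances relative to that analysis are:

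- post-training values: 1 (29 df)
- change: 2(1 − r) (29 df)
- ANCOVA: (1 − r²) × 28/27 (28 df), where 28/27 is the average cost of chance baseline imbalance at N = 31

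Example at r = 0.5: the ANCOVA factor is 0.75 × 28/27 = 0.778, so SE = 0.359 × sqrt(0.778) = 0.317 SD. The noncentrality is 0.8/0.317 = 2.52, against 0.8/0.359 = 2.23 for either unadjusted test.

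**Results** (noncentral t, with ANCOVA power averaged over chance imbalance; triplets are post-training / change / ANCOVA). Equivalent N is the number of patients the better unadjusted analysis needs to match the variance of ANCOVA on 31, that is 31 × its factor ÷ the ANCOVA factor.

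| r | Variance factor | Power at 0.8 SD, % | Gain over better unadjusted, points | Detectable at 80% power, SD | Equivalent N |
|---|---|---|---|---|---|
| 0.2 | 1 / 1.60 / 0.996 | 57.6 / 39.8 / 57.8 | 0.2 | 1.04 / 1.32 / 1.04 | 31.1 |
| 0.3 | 1 / 1.40 / 0.944 | 57.6 / 44.4 / 60.0 | 2.4 | 1.04 / 1.23 / 1.01 | 32.8 |
| 0.5 | 1 / 1.00 / 0.778 | 57.6 / 57.6 / 68.4 | 10.8 | 1.04 / 1.04 / 0.92 | 39.9 |
| 0.7 | 1 / 0.60 / 0.529 | 57.6 / 79.3 / 84.0 | 4.7 | 1.04 / 0.81 / 0.76 | 35.2 |
| 0.8 | 1 / 0.40 / 0.373 | 57.6 / 92.5 / 94.0 | 1.5 | 1.04 / 0.66 / 0.64 | 33.2 |

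**Break-evens.** ANCOVA beats post-training values when (1 − r²) × 28/27 < 1, so r > sqrt(1/28) = 0.189. It beats change when (1 + r) × 28/27 < 2, so r < 54/28 − 1 = 0.929. Outside that range it loses slightly: 56% against 58% power at r = 0, and a detectable difference of 0.332 against 0.329 SD at r = 0.95. Simulation with 60,000 normal-data trials per setting gave type I error of 4.8–5.2% and the same power to within about a point.

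**Non-parametric route.** Simulated power (30,000 trials per setting, 0.8 SD shift and r on the latent scale; type I error 4.7–5.2%) for Mann-Whitney on post-training values / Mann-Whitney on change / rank ANCOVA:

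| r | Lognormal outcome, % | Ordinal 0–10 score with a floor, % |
|---|---|---|
| 0.3 | 55 / 45 / 58 | 54 / 43 / 56 |
| 0.5 | 55 / 57 / 65 | 54 / 54 / 63 |
| 0.7 | 55 / 76 / 79 | 55 / 75 / 77 |
| 0.8 | 56 / 89 / 90 | 55 / 88 / 87 |

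Separately coded repeats agreed to within about 3 points, so small differences in this table should not be over-read.

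**If allocation was not random.** Take no treatment effect and a true baseline gap D. If the gap is stable, the biases are D / 0 / (1 − r)D. If it regresses to rD, they are rD / −(1 − r)D / 0. At D = 0.5 SD and r = 0.5 the stable gap gives 0.50 / 0 / 0.25 SD (false-positive rates 27 / 5 / 11%). The regressing gap gives 0.25 / −0.25 / 0 SD (10 / 10 / 5%).

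**The case against.** The strongest reply is that nothing here is an error. The unadjusted test is valid, and choosing ANCOVA is a matter of efficiency. Random allocation, on which the precision argument rests, is not documented; without it ANCOVA can itself be biased, and more so than change when a baseline gap is stable. The gain over the better unadjusted option is near zero at r = 0.2 and only 1–2 points at r = 0.8, and 0.8 SD is an arbitrary effect. At 0.5 SD and r = 0.5, ANCOVA raises power only from 27% to 33%. Rank ANCOVA gives no difference in outcome units and no confidence interval.

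All of this is accurate, and it sets the weight of the point without removing it. The better unadjusted option cannot be picked without knowing r, and a wrong pick is expensive: at r = 0.7, post-training values give 26 points less power than ANCOVA (84.0 − 57.6), and at r = 0.2 change gives 18 points less (57.8 − 39.8). The worst power cost of ANCOVA against post-training values is about 1.5 points, at r = 0. The 0.19–0.93 range belongs to the normal-data model; for ordinal scores at r = 0.8 rank ANCOVA is level with change or about a point below it. Rank ANCOVA's lack of an interval is real, but the SAP plans no interval with the Mann-Whitney test it would replace.

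**Conclusion.** The concern holds. The plan names only an unadjusted between-arm test, does not name the variable tested, and uses no baseline covariate although its paired tests imply that baseline values exist. Under random allocation and the normal equal-SD model with 16 versus 15 patients, ANCOVA is more precise than either reading of the effect test for r between about 0.19 and 0.93. At a true effect of 0.8 SD the gain over the better unadjusted choice peaks at about 11 points of power near r = 0.5, where that choice would need 40 patients to match ANCOVA on 31.

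This is a loss of precision and an unnamed estimate, not an invalid analysis; it should be fixed but is not fatal. I am confident that no adjustment is planned. The size of the benefit depends on r and on the allocation method, neither of which the documents give. If allocation was not random, bias rather than precision becomes the main issue.

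**What to change.** - State which variable the between-arm test uses and when it was measured, and state how patients were allocated.
- For each continuous outcome, make the between-arm analysis an ANCOVA of the post-training value on arm and the baseline value of the same outcome. Report the adjusted difference with its 95% CI, and keep the unadjusted comparison as secondary.
- List by name the outcomes to be analysed non-parametrically, and use rank ANCOVA on baseline in place of the unadjusted Mann-Whitney test.
- If allocation was not random, report both ANCOVA and change-score results, with the caveat that they can estimate different effects and neither is assured unbiased.
- Outcomes recorded only as present or absent are outside this change and need a different model.

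The cost is one degree of freedom per model and no new data, provided baseline values exist. Precision falls slightly if r is below about 0.19 (against post-training values) or above about 0.93 (against change). Both documents are written in the past tense: if the analysis has been done, this is a re-analysis to be labelled post hoc; if not, only the SAP wording changes.
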